6.3. Reporting of serious adverse events	27
6.4. Safety reporting to Health Authorities and Ethics Committees.....	27
7. Data management and data quality control	28
7.1. Source data	28
7.2. Data collection and documentation	28
7.3. Ethical, legal and security issues	29
7.4. Data storage and preservation	30
7.5. Definition of reference language – translation of study documents.....	30

8. Statistics.....	30
8.1. Definition of primary endpoint.....	30
8.2. Justification of number of trial participants.....	31
8.3. Description of statistical methods	31
9. Duties of the investigator	32
9.1. Investigator's confirmation	32
9.2. Damage coverage.....	32
9.3. Project management.....	32
10. Ethical considerations.....	33
10.1. Independent Ethics Committee (IEC)	33
10.2. Evaluation of the risk-benefit ratio	33
10.3. Participant information and consent	33
10.4. Participant confidentiality	34
10.5. Participants requiring particular protection	34
10.6. Other aspects.....	34
11. Quality control and quality assurance	35
11.1. Monitoring and auditing.....	35
11.2. Data and safety monitoring board (WHO) / data monitoring committee (EU/FDA)....	35
12. Dissemination of results and publication.....	35
13. References.....	36

IV. Synopsis

Study Title	Efficacy and safety of moxidectin in comparison to ivermectin against Strongyloides stercoralis infection in adults: a randomized controlled non-inferiority trial
Study Acronym	StrongMoxi
Study Type	Phase 3 trial
Sample size	350
Indication	Strongyloides stercoralis infection
Investigational Product and Reference Treatment	Investigational product: moxidectin Reference treatment: ivermectin
Protocol Number, Date and Version	1, 10.02.2022, v1.02
Trial registration	Registered on https://www.clinicaltrials.gov/ (NCT04848688)
Study Rationale	To provide evidence on: Efficacy and safety of an 8 mg dose moxidectin compared to 200 µg/kg dose ivermectin in adults against infection with S. stercoralis in Cambodia.
Study Objectives	To determine the efficacy and safety of: 8 mg of moxidectin in comparison to the standard treatment dose of ivermectin (200 µg/kg) in adults infected with S. stercoralis . Our primary objective is to demonstrate non-inferiority in terms of CR against S. stercoralis in adults of an oral 8 mg of moxidectin compared to 200 µg/kg of ivermectin. The secondary objectives of the trial are: 
 1) to evaluate the safety and tolerability of moxidectin 2) to compare the larval reduction rate (LRR) of the two different treatments against S. stercoralis 3) to evaluate the CRs of the different treatments against STH co-infections 4) to investigate potential extended effects on follow-up helminth prevalence at 42-49 and 63-70 days post-treatment 5) to relate socioeconomic characteristics (SES), access to sanitation, water facilities, hygiene to baseline infection intensity

	
6) to determine the larval excretion pattern until day 28, determined at every second day between day 0 and 28 post-treatment in a subset of 50-100 adults
 
7) to determine the origin of remaining worm burden after treatment to treatment failure and reinfection based on genetic profiling

Study design	Randomized controlled, double-blinded, 2-arm, parallel group, non-inferiority trial
Study product / intervention	Administration of an oral single-dose of moxidectin (8 mg), or an oral single-dose of ivermectin (200 µg/kg)
Comparator(s)	Ivermectin (200 µg/kg)
Key inclusion / Exclusion criteria	
Inclusion: Adults (\geq 18-65 years) infected with S. stercoralis.
 
Exclusion: Any abnormal medical conditions, negative diagnostic result for S. stercoralis, no written informed consent by individual. Pregnancy, lactating or planning to become pregnant within the next six months.

Primary Endpoints	CR against S. stercoralis at 14-21 days post-treatment derived from larvae per gram (LPG) assessed by quantitative sextuplet Baermann.
Secondary Endpoints	
 - LRRs against S. stercoralis assessed 14-21, 42-49 and 63-70 days post-treatment by quantitative sextuplet Baermann or every second day between day 0 and day 28 by quantitative duplicate Baermann (50-100 adults) - Adverse events - CRs against T. trichiura, A. lumbricoides, hookworms or Taenia ssp. assessed 14-21 days post-treatment by quadruple Kato-Katz - Genetic profiling of all S. stercoralis positive participants (first stool sample at each time point)
Exploratory Endpoints	None
Interim Analyses	None
Study Duration	12 months in total, 16 weeks per participant
Schedule	03/2022 of first-participant in (planned) 02/2023 of last-participant out (planned)
Measurements & procedures	Three stool samples will be collected at baseline analysed in duplicates by a quantitative Baermann method for S. stercoralis infection. Co-infection with T. trichiura , A. lumbricoides , hookworm or Taenia ssp. will be identified using duplicate Kato-Katz thick smears on two stool samples. The medical history of

	
the participants will be assessed with a standardized questionnaire, in addition to a clinical and physical examination carried out by the study physician shortly before treatment day. Each participant will be asked to provide a finger-prick blood sample for haemoglobin measurements at baseline. Enrolled participants will be treated with either 8 mg of moxidectin or with the standard treatment ivermectin (200 µg/kg).
 
The adults will be interviewed a) before treatment, 3 and 24 hours as well as 14-21, 42-49 and 63-70 days after treatment about the occurrence of adverse events. The efficacy of the treatment will be determined 14-21 days post-treatment. All stool samples will be examined with quantitative sextuplet Baermann assays and quadruplet Kato-Katz thick smears.
 
At 42-49 and 63-70 days post-treatment another three stool samples will be collected and quantified for S. stercoralis larvae using Baermann assay to assess potential long-term benefits of the study drugs and treatment regimen. From all positive S. stercoralis cases, the larvae will be stored in 70% ethanol and shipped to Australia for sequencing. Of 50-100 adults additional stool samples will be collected every second day between treatment and 28 days post-treatment to evaluate larval secretion patterns.
 
To all participating households, a brief questionnaire will be administered assessing information on socioeconomic characteristics (SES) and access to sanitation, water facilities, and hygiene behaviour.

Statistical Analyses	
An available case analysis (full analysis set according to the intention to treat principle) will be performed, including all participants with primary endpoint data. Supplementary, a per-protocol analysis will be conducted.
 
CRs will be calculated as the percentage of larvae-positive participants at baseline who become larvae-negative after treatment, assessed 14-21 days post-treatment by sextuplicate Baermann. Uncertainty estimates around the differences among CRs will be assessed using melded confidence intervals with mid-p correction. The non-inferiority margin is set to a 10%-points absolute difference in CR.
 
CRs of coinfections will be calculated as the percentage of egg-positive participant at baseline who become egg-negative after treatment, assessed 14-21 days post-treatment with quadruple Kato Katz assays.
 
LPG will be assessed by calculating the mean of the larvae counts from the Baermann assays and divided by the mean weighted amount of these stool samples. The LRR will be calculated following: (LRR = (1-(LPG at follow-up/LPG at baseline))*100).
 
Geometric and arithmetic mean larvae counts will be calculated for the different treatment arms before and after treatment to

	assess the corresponding LRRs. Bootstrap resampling method with 5,000 replicates will be used to calculate 95% confidence intervals (CIs) for LRRs and differences between LRRs. Adverse events and efficacy outcomes stratified by infection intensities will be compiled into frequency tables and compared between treatment groups using descriptive summaries.
GCP statement	This study will be conducted in compliance with the protocol, the current version of the Declaration of Helsinki, ICH-GCP E6 (R2) as well as all national legal and regulatory requirements.
Recruitment procedure	The trial will be conducted in Cambodia in adults aged 18-65. It will take place in areas with moderate to high infection risk in Kampong Chhnang province (prevalence: approx. 41.5%, identified from earlier studies and/or based on experience of the local collaborating teams).
Coverage of damages	Policy No: D/001/CPID/21/000002
Storage of data and samples for future research aims	After the study has been completed, all samples will be destroyed and case report forms, informed consents, source data and trial master file will be kept for a minimum of 15 years (chapter 10).
Conflict of interest in relation to the investigated drugs	We declare no conflict of interest in relation to the investigated drugs.

Abbreviations

AE	Adverse event
CI	Confidence interval
CR	Cure rate
CRF	Case report form
DALYs	Disability-adjusted life years
DF	Dose finding
DSMB	Data and safety monitoring board
EKNZ	Ethikkommission Nordwest- und Zentralschweiz
GCP	Good clinical practice
GLP	Good laboratory practice
Hb	Haemoglobin
ICH	International council for harmonization of technical requirements for pharmaceuticals for human use
IEC	Independent ethics committee
LPG	Larvae per gram
LRR	Larvae reduction rate
NTD	Neglected tropical disease
PI	Principal investigator
RDT	Rapid diagnosis test
SAE	Serious adverse event
STH	Soil-transmitted helminths
WHO	World Health Organization

2. Background information

Over the last decades, increasing evidence has linked major neglected tropical diseases (NTDs) to significant adverse impacts on human and economic development. NTDs affect more than one billion people globally, in particular poor, and marginalized tropical populations, and contribute to an estimated 3.3 million disability-adjusted life years (DALY) lost globally. NTDs also include soil-transmitted helminthiasis such as strongyloidiasis, which is the target of this clinical study [1].

Strongyloides stercoralis is a soil-transmitted nematode belonging to the most neglected infections among the NTDs and found almost worldwide, though with largest prevalence in tropical and subtropical regions, as an example Cambodia [2-4].

Infectious larvae are found in humid soil that is contaminated with faeces. Upon penetration of the intact skin of their host, *S. stercoralis* can reproduce within their human host. This endogenous autoinfection may result in long-lasting infections, which is not seen in other soil-transmitted helminth (STH) infections. Furthermore, *S. stercoralis* is known for its unique and threatening feature to cause systemic infection, which can persist for a lifetime, if appropriate therapy is not administered. *S. stercoralis* infections are typically most intense and debilitating in adults causing significant morbidity [6-8]. However, most infections, particularly chronic low-intensity infections remain non-specific and might be expressed as suffering from malnutrition, physical and cognitive retardation, and reduced work performance [5].

Chemotherapy combined with health education and water, sanitation and hygiene (WASH) programs remain the core to reduce the serious health impacts. The currently advocated treatments by the World Health Organization (WHO) are a single dose of ivermectin or multiple doses of albendazole, while albendazole is less efficacious compared to ivermectin [9, 10]. Since drug pressure is high and resistance is a threat it is of uttermost importance to develop new treatment alternatives. Among new candidates in the human antihelminthic drug development pipeline, moxidectin, a macrocyclic lactone might be a promising alternative. Moxidectin has been recently approved by the Food and Drug Administration (FDA) for use against onchocerciasis (<http://www.who.int/tdr/news/2018/moxidectin-approved-as-treatment-for-river-blindness/en/>) [11]. Moxidectin offers some advantages over ivermectin. First of all, moxidectin is used weight independent (for onchocerciasis at an 8 mg fixed dose), which renders the administration easier to handle, especially when treating large communities. Second, moxidectin has been shown to have a lower neurotoxic potential than ivermectin [12]. Thirdly, the pharmacokinetic profile of moxidectin in healthy individuals (very long $t_{1/2}$, and a large Vd/F , compared to ivermectin) arises prospects for efficacy also against long-term parasitic activity – as is particularly important when treatment of *S. stercoralis* is desired [13].

Finally, most importantly moxidectin has been successfully used in veterinary medicine against certain ivermectin-resistant strains [14].

Moxidectin was evaluated as an extremely safe drug. A single-dose of 36 mg moxidectin in healthy adults was the highest dose tested to date that still represented a well-tolerated dose [13]. The 1 x 8 mg, therefore, selected, as the highest dose in our study will not pose any health risk. Most common side effects include hypotension, itching, headache, abdominal pain, fever, dizziness or diarrhea. Serious or even fatal encephalopathy may occur in patients co-infected with *Loa Loa*. Furthermore, moxidectin is known to worsen onchodermatitis in patients with hyperactive onchodermatitis. Cambodia is not endemic neither for *Loa Loa* nor onchodermatitis and thus these symptomatic advents shall not constitute a risk in our study. Nevertheless, patients with symptoms for onchodermatitis will be excluded from the study. Additionally, although conclusive teratogenic data on moxidectin are missing, decreased fetal survival and increased fetal born with malfunctions is observed in some animals studies. Thus, pregnant patients as well as females planning to become pregnant within the next six months will strictly be excluded. Last, owing to the lipophilic nature of moxidectin, extraction of moxidectin to the breast milk of nursing mothers is very likely and could be demonstrated in lactating cows [15]. The risk of moxidectin in nursing infants is though unknown, thus breastfeeding females will also be excluded in this study.

In a small exploratory study using the veterinary formulation, a single-dose of 8 mg of moxidectin, and a small sample size (127 participants) moxidectin has been found to be efficacious against *S. stercoralis* (cure rates of 93.7%) and well tolerated in participants [16]. The follow-up phase 2a, randomized, placebo-controlled, dose-escalation trial conducted this year in northern Lao PDR evaluated the efficacy and safety of 2 mg to 12 mg of the human formulation of moxidectin in 209 participants. All tested moxidectin doses showed a promising tolerability with no safety concerns. 4-12 mg of moxidectin displayed a good efficacy profile in the treatment against *S. stercoralis* infections in adults (CR of 83.1%-88.3%). Since the 8 mg dose (CR of 87.0%; 95% CI: 79.8-91.9) is used for onchocerciasis and currently evaluated for other helminth infections this dose was recommended to take forward in phase 2b and phase 3 trials.

In this trial, we will test for non-inferiority of the recommended 8 mg of moxidectin against the standard dose of 200 µg/kg ivermectin.

Moreover, there is a need to explore whether the longer half-life of moxidectin ($T_{1/2}$: 491-832 h) compared to ivermectin ($T_{1/2}$: 16-32 h) could reveal a benefit in the treatment of *S. stercoralis* infections [13, 22]. Potential extended effects will be examined through a prolonged efficacy, safety and tolerability assessment scheme. Thus, additional follow-ups (besides the standard 14-21 days) will be conducted, namely 42-49 days post-treatment in correlation to the duration

of an autoinfection cycle and 63-70 days post-treatment analogous to a second auto-infection cycle as well as the elimination time of moxidectin from blood [13, 23].

Besides the study will be complemented by displaying larval excretion pattern over the whole time course after treatment until 28 days post-treatment and guide more appropriate follow-up periods. The appropriate follow-up time points are today not evaluated for infections with *S. stercoralis*.

Last, strongyloidiasis cannot solely be fought with chemotherapy, yet there is a need for multifaceted approaches including environmental and behavioral adaptation to attain disease control and elimination [30]. This study will be complemented by assessing socioeconomic characteristics, access to sanitation and water facilities as well as hygiene to identify influencing factors with regard to infection intensity and reinfection [30, 31].

Ultimately, results from this trial will inform decision on how moxidectin could be used to treat strongyloidiasis on a patient level and evidence will be strengthened to include moxidectin in the drug armamentarium for future community-wide chemotherapy.

3. Trial objective and purpose

The primary study objectives are

To determine if the efficacy in terms of cure rate of an oral 8 mg of moxidectin is non-inferior to the standard dose of a single oral ivermectin application (200 µg/kg), in 350 *S. stercoralis*-infected adults in Cambodia.

The secondary study objectives are

- 1.) to determine safety and tolerability of an oral moxidectin dose in 175 adults infected with *S. stercoralis*.
- 2.) to compare the efficacy based on larvae reduction rates of the different treatments drugs and regimens in 350 adults infected with *S. stercoralis*.
- 3.) to evaluate the CRs of the different treatments against STH co-infections.
- 4.) to investigate potential extended effects on follow-up helminths prevalence of the different treatment drugs and regimens around 42-49 and 63-70 days post-treatment.
- 5.) to relate socioeconomic status (possession of indicator assets), access to sanitation, water facilities and hygiene to baseline infection intensity.
- 6.) to assess the larval excretion pattern of *S. stercoralis* after treatment with moxidectin up to 28 days post-treatment.
- 7.) to assess the origin of the larvae positive stool samples by genetic profiling.

4. Methodology

4.1. Primary and secondary endpoint

CR is the primary endpoint. In addition, LRR will be determined and safety and tolerability of treatment evaluated (secondary endpoints). CRs against co-infections are considered as exploratory endpoints.

4.2. Type of trial

Double-blinded, randomized controlled parallel group trial (non-inferiority between 8 mg of moxidectin versus ivermectin, 200 µg/kg) with masked primary outcome assessors.

4.3. Trial design

A randomized trial will be conducted with two treatment arms to be followed-up over a 14-21 follow-up period with additional assessments at 42-49 and 63-70 days after treatment. The trial

will test for non-inferiority of a 8 mg dose of moxidectin versus ivermectin 200 $\mu\text{g}/\text{kg}$ with a margin of 10%-points.

The study cohorts are presented in the figure below:

[figure not shown]

Figure 1. Design and timeline of the non-inferiority trial to be implemented. A loss to follow-up of 10% is assumed.

4.3.1. Diagnosis

At baseline, all participants will be asked to provide three stool samples. The stool samples will be collected until a total of approximately 400 *S. stercoralis*-infected adults are registered, which assumes a lost to follow-up of 10%. As diagnosing very low-intensity chronic infections remains a major challenge for quantitative and qualitative analysis for *S. stercoralis*, Baermann assays will be done in duplicates and the average over three stool samples will be taken for analysis [36, 37].

To this end, a quantitative Baermann funnel concentration technique will be used for the quantitative assessment of *S. stercoralis* infections [37-39] using stool samples from three different days. The stool samples will be warmed in a water bath to 36°C. A 5 g stool sample will be placed on gauze inserted into a glass funnel and covered with temperature 36°C water. Following two hours of artificial light exposure, the collected liquid will be centrifuged and the sediment prepared for analysis by microscope [40, 41].

Moreover, from the first two stool samples from each participant a duplicate Kato-Katz thick smear will be prepared to detect co-infections with any of the three major STHs, namely *A. lumbricoides*, *T. trichiura* and the hookworms as well as *Taenia* ssp. [42]. In case we identify positive *Taenia* ssp. cases stool samples will be used for the further development of new diagnostic tools.

The slides from the Baermann and Kato-Katz thick smears will be analyzed under a microscope by experienced technicians and a subsequent independent quality control of sample results (approximately 10%) will be conducted. *S. stercoralis* larvae will be counted quantitatively. Co-infections with STH eggs will be recorded qualitatively for the different species and assigned as egg positive or negative. Results are considered correct if the following tolerance margin is not exceeded: (i) No difference in presence/absence of each species separately for counts ≥ 1 egg/larvae, (ii) larvae counts are $+\/-10\%$ larvae for counts ≤ 100 larvae or $+\/-20\%$ for counts > 100 larvae [43]. In case discrepancies above the tolerance margin are noted, slides are re-read by the local technicians. The new results are discussed, so that in case of discordant results, slides can be re-evaluated to reach consensus. Infection intensity expressed as the arithmetic and geometric mean larvae count per gram of stool will be calculated. All microscopically analyzed Baermann samples as well as the Kato-Katz thick smears will be destroyed after passing the quality control.

The same sampling procedure and diagnostic approach will be applied at the defined follow-up time points.

4.3.2. Clinical examination

A clinical examination of the study participants assessing general health, anthropometric parameters including height and weight as well as frontal temperature using an frontal no-touch thermometer will precede the treatment. Each participant will be asked to provide a finger-prick blood sample for haemoglobin (Hb) levels, which will be detected using a HemoCue analyzer (Hb 301 system, Angelholm, Sweden). To avoid accidental treatment of pregnant women all female participants will be asked to provide a urine sample to be subjected to a pregnancy rapid diagnostic test at baseline. Women will be strongly advised to avoid becoming pregnant during the entire study period. All trial participants will further be asked about existing clinical symptoms before drug administration.

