4.3.3. Adverse effects assessment

Participants will be kept for 3 hours after treatment administration to observe any possible acute adverse events (AEs) and re-assessment will be done at 24 hours post-treatment. Additionally, interviews will be conducted to determine the emergence of clinical symptoms such as headache, abdominal pain, itching, nausea, vomiting and diarrhea directly before treatment within the scope of baseline assessment. At 3 and 24 hours after treatment and retrospectively at days 14-21, 42-49 and 63-70 days post-treatment, participants will again be interviewed for the assessment of adverse events. Symptoms arising within the time span of 14 days after treatment and the respective follow-up time points will be monitored actively by local health workers who will report incidences to the study team. Any symptoms will be recorded in the case report form (CRF) and immediate action will be pursued if indicated.

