4.6. Schedule of visits

Table 1. Schedule of visits

	Screening / Baseline / Treatment / Safety					Follow-up period		
	Day -90	Day -3 - 0	0 h	1-3 h	24 h	Day 14-21	Day 42-49	Day 63-70
Informed consent	X							
Diagnosis (stool exam) ^(a)	X					X	X	X
Baseline data ^(b)	X							
Questionnaire	X							
Medical history ^(c)		X						
Clinical examination ^(d)		X						
Physical examination ^(e)		X						
Randomization administration of treatment			X					
Capturing AEs ^(f)				X	X	X	X	X
Capturing SAE ^(f)				X	X	X	X	X

^(a) based on duplicate Baermann assays of three stool samples. Daily stool sample will take place in 50-100 adults between day 0 and day 28.

^(b) date of birth, age, sex, height, weight, body temperature, pulse rate, blood pressure, Hb measurement, pregnancy test and recording of breastfeeding.

^(c) information gained by asking specific questions concerning chronic disease and concomitant medications.

^(d) investigation for signs of disease: head ache, abdominal pain, nausea, vomiting, diarrhea, itching, other symptoms.

^(e) physical examination on ear, nose, throat, eyes, lungs, lymph nodes and skin.

^(f) a standardized symptom questionnaire is used, that includes the recording of headache, abdominal pain, itching, nausea, vomiting, diarrhea, allergic reaction, others.

5. Selection of the trial participants

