6.1.5. Serious adverse events

According to the ICH “Clinical Safety Data Management: Definitions and standards for expedited Reporting E2A”

(https://www.ich.org/fileadmin/Public_Web_Site/ICH_Products/Guidelines/Efficacy/E2A/Step4/E2A_Guideline.pdf) a serious SAE includes any event (experience) or reaction in any untoward medical occurrence that at any dose:

1. is fatal, results in death;

2. is life threatening, meaning, the participant was, in the view of the investigator, at immediate risk of death from the reaction as it occurred, i.e., it does not include a reaction that, had it occurred in a more serious form, might have caused death;
3. is a persistent or significant disability or incapacity, i.e., the event causes a substantial disruption of a person's ability to conduct normal life functions;
4. requires, or prolongs in-patient hospitalization;
5. is a congenital anomaly or birth defect;
6. is an important medical event, based upon appropriate medical judgment, that may jeopardize the patient or participant or may require medical or surgical intervention to prevent one of the other outcomes defining serious.

A “severe” AE does not necessarily meet the criteria for a “serious” AE. Serious adverse events are reported from the first dose of study medication to 21 days post-treatment.

SAEs that are still ongoing at the end of the study period will be followed up to determine the final outcome. Any SAE that occurs after the study period and is considered to be possibly related (definitions will be used according to the WHO-UMC system; see: <http://who-umc.org/Graphics/24734.pdf>) to the study treatment or study participation will be recorded and reported immediately.

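### The one pregnancy test may fall up to about 12 weeks before dosing, and no listed item after dosing asks about pregnancy or follows one to its outcome

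*Combined protocol and SAP*

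**What the plan says.** **Before dosing.** Section 4.3.2 gives both the aim and the test: "To avoid accidental treatment of pregnant women all female participants will be asked to provide a urine sample" for a rapid test at baseline. Table 1 (Section 4.6), footnote (b), lists "pregnancy test and recording of breastfeeding" among the baseline data, and that row is marked only at Day -90. Section 4.5 says that screening begins 12 weeks ahead of treatment. Other text points closer to dosing. The synopsis has the clinical and physical examination "carried out by the study physician shortly before treatment day", Table 1 puts the clinical examination at Day -3 to 0, and Section 4.3.3 places the symptom interview "directly before treatment within the scope of baseline assessment".

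**After dosing.** Section 4.3.2 says: "Women will be strongly advised to avoid becoming pregnant during the entire study period". Table 1 lists only stool diagnosis and AE/SAE capture at the follow-up visits. On AE capture, footnote (f) says: "a standardized symptom questionnaire is used, that includes the recording of headache, abdominal pain, itching, nausea, vomiting, diarrhea, allergic reaction, others".

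**Section 6.** Pregnancy is not mentioned. One SAE criterion in 6.1.5 is that the event "is a congenital anomaly or birth defect". That section ends SAE reporting at day 21, while Table 1 captures SAEs up to day 63-70. SAEs after the study period are reported if judged possibly related. Section 6.3 also requires 24-hour reporting of unanticipated study-related problems that put participants or other people at risk.

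**Exclusions.** The synopsis and Section 2 exclude women who plan a pregnancy in the coming six months. The operative criterion in 5.3 covers only the study period.

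**The concern.** Section 2 gives the reason for caution: some animal studies show reduced fetal survival and malformations, and conclusive teratogenicity data for moxidectin are missing. It also gives moxidectin a half-life of weeks. Two exposures follow.

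First, a woman could test negative at screening, conceive, and then be dosed, which is what the test in 4.3.2 is meant to prevent.

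Second, a woman could conceive during follow-up with drug still present. Nothing listed would reveal that pregnancy, and no rule would track it. Excluding women who plan a pregnancy does not reach unplanned conceptions. At stake are the safety of a few women and fetuses, and the loss of information that the sponsor itself says is lacking.

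**Working it through.** **1. Gap between test and dose.** The documents give no single figure.
- Table 1 and Section 4.5: Day -90, or 12 x 7 = 84 days, at the most.
- Synopsis: "12 months in total, 16 weeks per participant". 16 x 7 = 112 days, and 112 - 70 = 42 days before dosing. This conflicts with the 84-90 days above, so it is not a usable upper limit.
- Sections 4.3.2 and 4.3.3 and the synopsis, read with the clinical-examination row of Table 1: 0-3 days.

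The gap is therefore between 0 and about 90 days, depending on which text the site follows.

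**2. Drug remaining after dosing.** Half-lives are from Section 2: moxidectin 491-832 h, ivermectin 16-32 h. Single-exponential decay is my assumption: fraction = 2^(-hours / half-life).
- Day 21 (504 h): 2^(-504/491) = 0.491; 2^(-504/832) = 0.657.
- Day 70 (1680 h): 2^(-1680/491) = 0.093; 2^(-1680/832) = 0.247.
- Day 180 (4320 h): 2^(-4320/491) = 0.002; 2^(-4320/832) = 0.027.
- Five half-lives: moxidectin 5 x 491/24 = 102 days to 5 x 832/24 = 173 days; ivermectin 3.3 to 6.7 days.

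On this model moxidectin is present throughout follow-up. Section 2 also links day 63-70 to elimination from blood, so the day-70 range should be read as approximate.

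**3. Can the birth-defect criterion operate?** Assume birth about 266 days after conception. Conception on days 0-70 gives birth on days 266 to 70 + 266 = 336, which is 266 - 70 = 196 to 336 - 70 = 266 days after the last visit. The late-SAE rule has no end date, but someone must know that the woman was pregnant.

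**4. How many?** The documents do not give the number of women, the share of child-bearing potential or a conception rate. As an illustration only, assume 40-60% women, 40-70% of them of child-bearing potential, and 0.2-1% conceiving per month (30.4 days). In the moxidectin arm of 175:
- Women of child-bearing potential: 175 x 0.4 x 0.4 = 28 to 175 x 0.6 x 0.7 = 73.5.
- Conceptions on days 0-70 (2.30 months): 28 x 0.002 x 2.30 = 0.13 to 73.5 x 0.01 x 2.30 = 1.69.
- Conceptions between test and dose if every woman had an 84-day gap (2.76 months): 28 x 0.002 x 2.76 = 0.15 to 73.5 x 0.01 x 2.76 = 2.03. With a 3-day gap (0.099 months): 0.006 to 0.07.

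The ranges span more than tenfold and are driven by the assumptions. They support only the statement that cases would be few.

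**The case against.** The best reply on timing is that 4.3.2 describes the test as part of an examination that precedes treatment, and that only one table row suggests Day -90. This is a fair reading and may be what the sites do. What stands is that staff work from the schedule, and the schedule gives the early date.

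On reporting, a reader might infer that a pregnancy could not be reported at all. The documents do not support that. The 24-hour rule in 6.3 can reasonably cover a known exposed pregnancy, a related birth defect found later is reportable under 6.1.5, and participants receive a card with telephone numbers (5.5). What remains is narrower: nobody is told to ask, and no outcome follow-up is set.

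The six-month planning exclusion is the main mitigation, and counted from dosing it outlasts five half-lives of moxidectin. However, 5.3 shortens it to the study period, and it concerns intentions only.

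A reader might also infer that giving ivermectin at day 70 to those still positive, without a repeat test, is a fault. The documents state no fetal risk for ivermectin, and 5.3 offers it even to people excluded from the trial, a group that includes pregnant women. A test and deferral there would delay standard treatment of an autoinfecting disease without a stated ground, so I do not ask for it.

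**Conclusion.** The point holds as a minor safety gap that is cheap to close. The schedule permits a pregnancy test up to about 12 weeks before dosing, contrary to the aim in 4.3.2, and after dosing the plan neither asks about pregnancy nor follows it to outcome. It would be too strong to say that women will be dosed on an old test, because the text conflicts and does not settle the timing. It would also be too strong to say that the trial has no pregnancy items anywhere, because the CRF, SAE form and consent pages were not available to check.

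The persistence figures (49-66% at day 21, 9-25% at day 70) rest on the stated half-lives and on simple first-order decay. The number of cases cannot be calculated from the documents, but should be small. The concern is mainly with the moxidectin arm, and the primary efficacy result is not affected.

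**What to change.** 1. In Table 1, place the urine pregnancy test at Day -3 to 0. Randomization is at 0 h, so a positive result excludes the woman before allocation.
2. Ask women of child-bearing potential about pregnancy at the three existing follow-up visits (days 14-21, 42-49 and 63-70).
3. In 6.3, make any pregnancy after dosing reportable, and follow it to outcome by phone or through a health worker.

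The cost is a protocol and CRF amendment, one question at visits that already take place, and occasional contact after day 70 for very few women, possibly beyond the planned 12 months. If the CRF or SAE form already contains these items, a cross-reference in Section 6 and the corrected table entry are enough.
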